6.5 Wk 10 Follow-up Visit Procedures

Subjects will return to the study site on an outpatient basis for a Follow-up Visit.

- Physical exam (abbreviated examination including body weight and evaluation of changes to previously observed abnormal findings)
- Vital signs and Active-Standing Test
- 12-lead ECG
- Serum hCG pregnancy test (females only)
- Clinical laboratory tests (to include hematology, serum chemistry, coagulation, HsCRP, and urinalysis)
- Record AEs
- Record concomitant medications

The Principal Investigator and study site staff should exert every effort to secure subject attendance to the Follow-Up visit. Three attempted telephone contacts should be documented by study personnel before a subject can be considered lost to follow-up. Furthermore, key research personnel should mail a certified letter to the subject's address if no response to 3 telephone contacts remain unanswered. If the subject or a family member does not respond, the certified letter receipt should be filed in the individual's research record with a copy of the letter sent.

7 DATA MANAGEMENT

7.1 Data Collection

All data will be collected according to the Sponsor or CRO's SOPs.

Upon database lock, to include resolution of all queries, the CRO, if applicable, will provide SAS Transport Files (SAS XPT) datasets to the Sponsor and to the biostatistician for analysis using secure electronic data transfer per the Sponsor's specifications.

7.2 Data Coding

7.2.1 Adverse Events

Adverse events will be coded using the Medical Dictionary for Regulatory Activities (MedDRA; version 18.0 or later) and tabulated, including categorical information of interest such as onset and resolution times, time of onset relative to dose, severity at onset, maximum severity, causal relationship to study medication, and action taken. Whenever possible, a constellation of signs and symptoms should be recorded as a unifying diagnosis (e.g., self-limited fever, runny nose, cough, and scratchy throat should be captured as an upper respiratory infection rather than by the individual signs and symptoms). Adverse events will be regarded as 'pre-treatment' if they occur between Screening and the time of administration of the first dose of study medication. All other AEs that occur after the first dose of study medication will be considered to be 'treatment-emergent'.

7.2.2 Concomitant Medications

Due to the variability in how medications are recorded, a standard naming convention is required in order to tabulate this data effectively. A common method of standardization is to categorize medications by their preferred term. In order to do this, medications will be coded using the WHO Drug Dictionary, Format C.

7.2.3 Medical History

Medical history will be coded using MedDRA (version 18.0 or later).

8 PLANNED STATISTICAL METHODS

The statistical analysis of the data obtained from this study will be the responsibility of the Sponsor or designated CRO. Full details of the statistical analyses will be written in a separate statistical analysis plan (SAP) which will be finalized prior to database lock. Any changes made to the pre-specified statistical analysis plan, will be listed in the Clinical Study Report along with an explanation as to why they occurred.

8.1 General Considerations

This is a proof-of-concept study design and there are no formal hypothesis tests being specified, Descriptive statistics for proportion based and continuous variables will be reported. Subgroup analysis by randomization stratification factor sex will be performed to assess potential safety and efficacy differences between males and females. Non-inferential between dose cohort comparisons for main study endpoint measures will be performed using parametric or non-parametric methods as appropriate and nominal p-values (2-sided) will be reported. The 95% confidence intervals for main study endpoint measures will also be reported.

8.2 Determination of Sample Size

No formal sample size and power calculation were performed. For this initial study in subjects it is planned to treat and complete safety and tolerability assessments in approximately 16 subjects, which is reasonable to assess the main study endpoints. Since subjects maybe replaced if they are withdrawn due to major protocol violations, a maximum of 20 subjects will be randomized in the study. It is expected that this number of subjects will provide guidance for the assessment of tolerability in this population and quantify the extent of abdominal pain relief.

8.3 Analysis Populations

The Safety Population will include all randomized subjects who received at least 1 dose of study medication.

The PK Completers Population will be defined as all subjects who receive APD371 and have at least 5 of the 9 scheduled PK collections on Wk 0 (Day 1), Wk 0 (Day 2) - 2 or Wk 8 (Day -1) and Wk 8, including the pre-dose sample.

The Efficacy population will include all randomized subjects who received at least 1 dose of study medication and have completed at least one consecutive week of APS up to Week 4.

8.4 Demographics and Baseline Characteristics

All screening subject characteristics of demographic data (age, height, weight, race/ethnicity), social history (smoking status, caffeine intake, alcohol intake), medical

history (abnormalities only), physical examination (abnormalities only), and concomitant medications at study entry will be listed for all subjects.

8.4.1 Demographics

Demographic data will be summarized and tabulated. Continuous variables will be summarized using number of observations (n), mean, standard deviation, median, minimum, and maximum. Frequencies and percentages will be reported for all categorical data.

8.5 Pharmacokinetic Variables

The PK analysis will be conducted by the Sponsor's representative or designated CRO employing noncompartmental methods

. Only subjects who are given active APD371 drug and have evaluable plasma concentration-time profiles will be included in the analysis.

Individual APD371 and metabolites M1 **Mathematical**, M2 **Mathematical**, and M4 (**Mathematical**) plasma concentrations at specified timepoints will be listed for each subject and will be summarized by dose level. Individual plasma concentration-time profiles of APD371 and metabolites M1, M2 and M4 will be plotted on both a linear and a semi-logarithmic scale for each dose level. Mean values will also be presented graphically for each dose level.

Pharmacokinetic parameters of APD371 and metabolites M1, M2, and M4 may be listed for each subject and summarized by dose level. The following PK parameters may be determined for APD371 and metabolites unless otherwise specified:

Wk 0 (Day 1) and Wk 8 (Day -1)		
C _{max}	maximum plasma concentration	
t _{max}	time of maximum plasma concentration	
AUC ₀₋₈	area under the plasma concentration-time curve over dosing interval (8 hours)	
Wk 0 (Day 2), 2, 4, 6, 8	3	
C _{trough}	plasma concentration observed before treatment administration during repeated dosing	

The individual elapsed sampling times will be used for all plasma PK parameters. For the purpose of calculating descriptive statistics and PK parameters, plasma concentrations below the lower limit of quantification (LLOQ) will be set to zero. After the peak, any measurable concentrations observed after two or more consecutive concentrations below the LLOQ will be considered anomalous and excluded from the PK analyses. Any quantifiable concentrations at pre-treatment on Day 1 will be set to zero.

Unrounded data will be used for estimation of summary statistics and PK analysis. Data will be rounded for reporting purposes only, with data presented to 3 significant figures for

numbers less than or equal to 1,000 and to the nearest integer for numbers greater than 1,000. Fold increases will be reported to two decimal places.

The ratio of each metabolite to APD371 will be calculated for C_{max} and AUC₀₋₈.

Summary statistics for continuous variables will include arithmetic mean, arithmetic SD, coefficient of variation, geometric mean, median, minimum and maximum; t_{max} will be summarized using median, minimum and maximum values. The effect of multiple doses of APD371 on PK parameters will be assessed with an analysis of variance model with treatment as factor. Appropriate transformations will be applied to the variables.

Ctrough APD371 will be summarized by treatment period for each subject.

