Dosage:	APD371 dosed at 25 mg or 100 mg three times daily (TID) at approximately $07:00 \pm 2$ hr, $15:00 \pm 2$ hr and $23:00 \pm 2$ hr for 8 weeks (Wk).
Concurrent Control:	Intra-subject screening (baseline)

[figure not shown]
Route and Formulation:	Oral, capsules which are identical for each dose
Objectives:	 Key Objective To assess the tolerability and safety of two doses of APD371 in subjects with Crohn's Disease (CD) experiencing abdominal pain treated for up to 8 Wk.
	 Exploratory Objectives: Determination of pharmacokinetic (PK) profiles (including metabolites) and average PK parameters (C_{max}, t_{max}, AUC₀₋₈) of two doses of APD371 TID Change in abdominal pain score (APS) from pre-dose (trough) to 1.5 hr post-dose (peak) following the first of 3 daily doses of APD371; assessed daily to Day 56 and averaged weekly to Wk 8
	 Change in average abdominal pain score (AAPS) from baseline to Wk 8 (averaged weekly to Wk 8) Proportion of subjects who are weekly responders Proportion of subjects who are end-of-treatment responders Number of pain-free days per week, based on responses to the Abdominal Pain Severity Pain medication use Effect of APD371 treatment on reduction in C-reactive protein (CRP) and other biomarkers at week 4 and week 8
Study Design:	 Effect of APD371 treatment on reduction in fecal calprotectin at week 4 and week 8
Sudy Design:	A randomized, open label, parallel group, multi center, comparison of two doses of APD371.Eligible subjects will enter a screening period of up to 4 weeks and will then be randomized in a 1:1 ratio to receive APD371 in doses of 25 mg or 100 mg TID for 8 weeks.

	Randomization will be stratified by sex.

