5.11 Pharmacokinetic Assessments

Pharmacokinetic samples for the assay of APD371 and metabolites M1 **1** , M2 , and M4 **1** will be collected will be collected at the visit time points indicated in the Schedule of Events (Table 1) and detailed in Pharmacokinetic sampling, Table 3.

Study Day	Blood sampling assessments*
Wk 0 (Day 1)	Prior to and 0.5, 1, 2, 4, 6, 8 (prior to second daily dose), 9
	and 10 hours post first daily dose.
Wk 0 (Day 2)	24 hours post dose first daily dose on Day 1

Wk 2	Prior to first daily dose
Wk 4	Prior to first daily dose
Wk 6	Prior to first daily dose
Wk 8 (Day -1)	Prior to and 0.5, 1, 2, 4, 6, 8 (prior to second daily dose).
Wk 8 (End-of-Treatment)	8 hours post dose first daily dose on Wk 8 (Day-1)

* Allowable windows for sample collection:

- time points up to 4 hours: \pm 5 mins

- time points after 4 hours: ± 15 mins

Total blood volume collected for PK samples will be approximately 100 ml.

A PK sample collection manual will be provided to instruct on the type of anticoagulant to be used, the material supplies, and the sample processing, storage, and shipping procedures.

Plasma samples will be stored at the local laboratory and shipped to the analytical lab for analysis.

At the end of each cohort, biological samples (e.g. plasma) should be packed, labeled, and shipped on dry ice to the designated bioanalytical CRO for analysis. Samples should be shipped in accordance with the hospital SOPs or guidance, and only on a Monday, Tuesday or Wednesday, to minimize the possibility of the samples being in transit over a weekend. If duplicate samples are being shipped, confirmation should be obtained of arrival at the analytical lab of one set of samples before the second set is shipped.

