6.3.2 Wk 0 (Day 1) Post treatment

- Vital signs and Active-Standing Test
- 12-lead ECG at 1.5 hours after initial Day 1 dose
- Abdominal Pain Score at 1.5 hr after first morning dose

- PK Blood samples for the analysis of APD371 and metabolite plasma concentrations 0.5, 1, 2, 4, 6 and 8 hr after the first daily dose (prior to second daily dose) and 9 and 10 hr.
- Record AEs;
- Record concomitant medications

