6.3.3 Wk 0 (Day 2)

- Vital signs and Active-Standing Test
- Abdominal Pain Scores
- A PK Blood sample for the analysis of APD371 and metabolite plasma concentrations will be collected 24 hr post first daily dose on Day 1 and before the first daily dose on Day 2
- Record AEs
- Record concomitant medications
- 6.3.4 Wk 0 to 8 (Day -1) (Days 1 to 56)
 - Abdominal Pain Scores will be determined three times a day.

6.3.5 End of Wk 1, 2, 4, 6

- Vital signs and Active-Standing Test
- Abdominal Pain Scores
- PK blood samples will also be taken immediately before the first daily dose (Week 2, 4 and 6 only)
- Clinical laboratory tests (to include hematology, serum chemistry, coagulation, HsCRP, and urinalysis) prior to first morning dose, Wk 4 only
- Study medication will be dispensed before the first daily dose for Wk 0 (Day 1), 2, 4 and 6
- Compliance will be assessed based on all returned bottles and treatment duration at Wks 2, 4, 6 and 8
- Record AEs
- Record concomitant medications
- Stool sample for fecal calprotectin (Wk 4 only)

It is important that subjects do not take their morning study medication prior to instruction by the investigation team on Wk 0 (Day 1 and Day 2), 2, 4 and 6.

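### The rule that excludes values after two below-LLOQ results does not restart at a new dose, so genuine 9 and 10 h concentrations on Day 1 can be removed

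*Protocol*

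**What the plan says.** Protocol 8.5 gives two rules for values below the LLOQ (BLQ).

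- **Substitution.** For descriptive statistics and PK parameters, "plasma concentrations below the lower limit of quantification (LLOQ) will be set to zero". Any quantifiable Day 1 pre-treatment value is also set to zero.
- **Exclusion.** "After the peak, any measurable concentrations observed after two or more consecutive concentrations below the LLOQ will be considered anomalous and excluded from the PK" evaluation. No dosing interval or day is named.

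The summary statistics required in 8.5 are "arithmetic mean, arithmetic SD, coefficient of variation, geometric mean, median, minimum and maximum", except for tmax.

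On Day 1, Protocol 6.3.2 schedules samples at "0.5, 1, 2, 4, 6 and 8 hr after the first daily dose (prior to second daily dose) and 9 and 10 hr". Table 3 in 5.11 adds one at "24 hours post dose first daily dose on Day 1", which 6.3.3 places before the first Day 2 dose. Section 8.5 lists Wk 0 (Day 2) among the Ctrough time points. Dosing is three times daily, at about 07:00, 15:00 and 23:00, each within 2 hours (Synopsis, Dosage).

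The supplied SAP has no BLQ rule. It refers PK to a standalone PK SAP dated 23 January 2019, which is not among the documents.

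**The concern.** The exclusion rule suits a profile after one dose, where a measurable value that reappears after two BLQ results is suspect. The Day 1 profile contains more than one dose. A rise at 9 and 10 h after BLQ results at 6 and 8 h is what the second dose should produce, yet the rule labels it anomalous.

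The loss is also selective. It falls only on subject-analyte profiles that drop below the LLOQ quickly, while BLQ results from other subjects at the same times stay in as zeros. The 9 and 10 h summaries and mean curves then describe a subset chosen by its own exposure. Section 8.5 covers the parent drug and three metabolites, so a low-exposure metabolite is the likeliest place for this to occur. Protocol 3.3 wants PK data that are reliable enough to guide later dose choice, and with 8 subjects planned per arm a few lost profiles would show.

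**Working it through.** The plan gives no figure to reproduce. The check applies the rule as written to the scheduled times.

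**1. Schedule.** Day 1 and Day 2 samples are at 0, 0.5, 1, 2, 4, 6, 8, 9, 10 and 24 h, ten in all. Nominal doses are at 0, 8 and 16 h. So 9 and 10 h are 1 and 2 h after dose 2, and 24 h is 8 h after dose 3.

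**2. Two readings of the peak.** Reading A takes the maximum within 0-8 h. Reading B takes the maximum over the whole 0-24 h profile.

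**3. Worked example (invented values, LLOQ = 5).**

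| Time (h) | 0 | 0.5 | 1 | 2 | 4 | 6 | 8 | 9 | 10 | 24 |
|---|---|---|---|---|---|---|---|---|---|---|
| Profile 1 | 0 | 40 | 100 | 80 | 12 | 3 | 1 | 75 | 60 | 6 |
| Profile 2 | 0 | 40 | 100 | 80 | 12 | 3 | 1 | 102 | 81 | 6 |

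In both profiles 6 and 8 h are BLQ. Profile 1 loses 9, 10 and 24 h under A and B. Profile 2 loses all three under A and none under B, because its overall maximum is then at 9 h. The undefined peak alone changes the result.

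**4. When the trigger occurs.** Assume log-linear decline from a peak at 1.5 h, the time at which the plan places its peak assessment. A value is BLQ by 6 h if half-life < (6 − 1.5) / log2(peak/LLOQ):

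- ratio 2: 4.5 / 1.00 = 4.5 h
- ratio 3: 4.5 / 1.585 = 2.8 h
- ratio 5: 4.5 / 2.322 = 1.9 h
- ratio 10: 4.5 / 3.322 = 1.4 h

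**5. Simulated share of subjects losing a 9 or 10 h value.** All inputs are assumptions: one-compartment oral model with superposition; typical absorption rate 2 per hour; log-scale SD 0.3 for half-life and per-dose exposure and 0.4 for absorption; 10% assay noise; exact 8 h spacing; 4,000 subjects per cell.

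| Half-life | A: Cmax/LLOQ 5 / 10 / 20 | B: Cmax/LLOQ 5 / 10 / 20 |
|---|---|---|
| 1 h | 95% / 78% / 54% | 49% / 41% / 28% |
| 2 h | 46% / 13% / 3% | 18% / 5% / 1% |
| 3 h | 12% / 1% / 0.2% | 3% / 0.3% / 0% |

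**6. Difference between arms.** If exposure is proportional to dose and the LLOQ is common, the 25 mg ratio is 25/100 = one quarter of the 100 mg ratio. Taking ratio 20 at 100 mg and 5 at 25 mg, with a 2 h half-life and reading A, the expected losses among 8 subjects are 0.03 × 8 = 0.2 and 0.46 × 8 = 3.7.

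**7. The 24 h sample.** A measurable 24 h value was lost in at most about 1.5% of subjects (A) or 0.1% (B). An analyte that is BLQ 8 h after dose 1 is usually BLQ 8 h after dose 3, and is then kept as zero. The dosing windows put dose 3 between 21:00 and 01:00 and the 24 h sample between 05:00 and 09:00, an interval of 4 to 12 h, so the real share could be higher.

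**8. Geometric means.** The geometric mean is the nth root of a product, so one zero makes it zero, and undefined on the log scale. At Day 1 pre-dose every value is zero by rule. Elsewhere a single BLQ result in an arm is enough, unless software drops zeros, in which case the figure covers only the quantifiable subjects.

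**The case against.** The strongest reply is that little of importance depends on the 9 and 10 h samples. The Synopsis bases dose-proportionality on Cmax and AUC0-8. AUC0-8 ends before dose 2, first-interval Cmax and tmax are fixed by then, and Wk 8 sampling stops at 8 h. Individual concentrations are still listed and plotted, so nothing leaves the record. PK is exploratory, and section 8.1 specifies no formal hypothesis tests. All of this stands and limits the point to descriptive Day 1 output, plus a Cmax taken beyond 8 h, which 8.5 does not rule out.

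A second reply is that the standalone PK SAP may already confine the rule. It may, but it cannot be assumed to do so. The protocol text is the only rule in view.

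A reader might go further and infer that every affected profile loses three of its ten samples, that Day 2 Ctrough is biased upward, or that a steady-state assessment is compromised. The documents do not support these. The usual loss is the 9 and 10 h pair. At 24 h the rule keeps zeros and removes measurable values, so an upward bias does not follow. Neither document gives the troughs a steady-state purpose.

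**Conclusion.** The point holds as a minor defect. Followed literally, 8.5 excludes genuine dose-2 concentrations at 9 and 10 h on Day 1 whenever an analyte is BLQ at 6 and 8 h after its peak. The distortion is confined to the 9 and 10 h summaries and mean profiles and to any Day 1 Cmax read beyond 8 h. Its direction is not fixed: removing low-exposure profiles raises a mean, while keeping zeros and removing measurable values lowers it.

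The mechanism follows from the text and the schedule alone. The frequency rests on assumed half-life and Cmax/LLOQ and could be nil. More loss in the 25 mg arm further requires roughly dose-proportional exposure and a common LLOQ.

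The geometric-mean conflict is certain at Day 1 pre-dose and conditional elsewhere. It concerns concentration and trough tables, not Cmax or AUC0-8 from quantifiable profiles.

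**What to change.** In 8.5, and in the PK SAP if it carries the same rule:

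- Apply the exclusion only within a single dosing interval, restart it at each dose, and define the peak separately for each interval.
- State that the 9, 10 and 24 h values are not excluded because of BLQ results in an earlier interval.
- Where any concentration or trough at a time point is BLQ, report the median and the number BLQ in place of the geometric mean.

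With the restart, exclusions from this cause fall to zero by construction and AUC0-8 does not change. If the PK SAP already does this, the sponsor need only confirm it. Protocol section 8 asks for changes to the pre-specified analysis to be explained in the study report, so the change should be recorded there.

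The cost is a few sentences and a rerun of the Day 1 concentration tables and plots. No new data are needed, and some geometric means will be shown as not calculated.

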8.6 Safety Analysis

8.6.1 Adverse Events

Adverse events will be coded using MedDRA v18.0 and tabulated by dose cohort, including categorical information of interest such as onset and resolution times, time of onset relative to dose, severity at onset, maximum severity, causal relationship to study medication, and action taken. AEs will be regarded as 'pre-treatment' if they occur between Screening and the time of administration of the first dose of study medication.

8.6.2 Physical Examinations

Physical examination results (abnormalities only) will be listed and summarized by dose cohort.

8.6.3 Vital Signs

Individual vital sign measurements will be listed by treatment and measurement time, and summarized using descriptive statistics. Summary statistics will also be provided for change from baseline in vital sign measurements by dose cohort.

8.6.4 Clinical Laboratory Values

Individual lab values will be listed by treatment and visit, and summarized by dose cohort using descriptive statistics. Summary statistics will also be provided for change from baseline in lab values. Shift tables from baseline to the last visit will also be produced for the laboratory assessments based on the categories of Low, Normal, and High.

8.6.5 12-lead ECGs

Individual 12-lead ECG values will be listed by dose cohort and visit, and summarized using descriptive statistics by dose cohort. Intervals to be provided for each ECG are: RR, PR, QRS, QT, QTc, QTcB, and QTcF. Any clinically significant change from baseline may be recorded as an AE if deemed appropriate by the Investigator or Sponsor.

8.7 Efficacy Analysis

8.7.1 Abdominal pain score (APS)

The change in APS scores between morning dose (trough) and 1.5 hr post-treatment first daily dose (peak) assessments will be summarized across all days of treatment and compared by dose cohort and overall. Difference between dose cohort will be reported.

8.7.2 Average abdominal pain score (AAPS)

AAPS will be summarized for the screening period and for each week of treatment before morning dose (trough) assessments and 1.5 hr post-treatment first daily dose (peak) assessments, by study cohort. Statistical comparisons of AAPS will be made between screening and WK 4 and at Wk 8, trough and peak assessments, by dose cohort and overall. Difference between dose cohort will be reported.

